## 8.0 Procedures Involved

8.1 *Describe and explain the study design.*

Randomized Control Trial. Subjects will be patients at Vistar Eye Center who are undergoing scleral buckle surgery for rhegmatogenous retinal detachment. Patients of this indication will be consented and enrolled in the trial as detailed in section 24, and randomized (by coin-flip) into one of two arms, the control or the experimental. Patients in both arms of the study will be screened for IOP via handheld digital tonometry (tonopen) and will undergo standard scleral buckle procedures, including irrigation with 1 ml .75% Marcaine for local anesthesia (as is standard for all surgeries). At time of surgery, patients in the experimental group will receive irrigation of 1 ml (40 mg/mL) triamcinolone around the bed of applied scleral buckle distributed equally in all 4 quadrants (.25 ml per quadrant) under the tenon layer of the eye. Patients in the control group will be given irrigation around the applied scleral buckle of 1 ml balanced salt solution instead of triamcinolone. Patients will be masked to the treatment group assignment. The surgeon cannot be masked, as the triamcinolone solution is white and the balanced salt solution is clear. Intraoperative details will be recorded in the EMR about the surgery in both groups, including duration of surgery, time of irrigation, any additional pharmaceuticals or anesthesia applied, procedures performed, and placement of the buckle. Patient will receive a pill-count form at the end of the visit to keep track of rescue analgesic consumption. All patients

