## Using Triamcinolone Acetonide to Reduce Pain after Scleral Buckle Surgery

will be given appointments for post-operative day 1, and 1-2 weeks post-operative as is standard practice.

On post-operative day one, primary outcome data will be obtained by a blinded examiner who will be giving the patient a form which asks about the patient's pain score by reference to an 11-point numbered rating scale (0-10). On the same form, patients will also be asked about post-operative nausea and vomiting for secondary endpoint, which will be scored from 0-6 by adding the points for question II and question III from the pain and nausea survey. The form will be collected by the same examiner when completed. Pill count sheet will be collected and additional sheet will be given for patient to track analgesic use between first and second visit.

Patient will then have regularly scheduled visit with the surgeon who will be screening the patient for success of surgery, adverse events, and will examine pain and nausea scores to ensure both are well controlled. The physician will be ensuring the patient's safety, and will be allowed to prescribe any medications deemed medically necessary for control of side effects, nausea, and pain. IOP of all patients will also be measured at this visit.

At second post-operative visit (1-2 weeks), patients' IOP will be measured again for safety endpoint. Patient pill count sheet will be collected.

Patients will be filling out 11-point NRS pain score and post-operative nausea and vomiting sheet again during office visit and it will be collected by blinded examiner. Patient will then be examined by surgeon again for success of surgery, adverse events, and control of pain and nausea.

	Before Surgery	Day of Surgery	Between Surgery and First Follow-Up Visit	First Follow-Up Visit (1 day after surgery)	Between 1 st and 2 nd Follow-Up Visits	Second Follow-Up Visit (1-2 weeks after surgery)	Long-Term Follow-Up (6 months )
Location	Clinic	Surgery Center	Home	Clinic	Home	Clinic	Phone
Procedures	The doctor will explain the study to patient	Everyone: Scleral Buckle Surgery. Experimental Group: Triamcinolone (steroid) will be applied during surgery. Control Group: Saline solution will		Everyone : will be examined by the doctor for safety		Everyone : will be examined by the doctor for safety	

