### 8.3 *What data will you collect during the study and how you will obtain them? Please include descriptions of electronic data collection, database matching, and app-based data collection.*

Patients will be assigned an arbitrary patient ID at beginning of the study which is recorded in the EMR. Demographic data about patient age, gender, and ethnicity will be extracted from the electronic medical record. No patient identifying data including name, addresses, date of birth, or

SSN will be extracted from the electronic medical record for the purpose of the analysis. Details of surgery will be extracted from the EMR.

During the study, IOP will be collected at two time-points via tonometer. This data will be extracted from the electronic medical record for analysis. Pain level via 11-pt NRS will be collected at two time points by survey. Data about analgesic consumption will be collected via survey form at two time points by survey. Nausea and vomiting score will be collected at two time points by survey. This data will be matched to de-identified patient ID. Physical survey forms will then be confidentially discarded.

*8.4 Who will transcribe or code audio and/or video recordings?*

N/A

*8.5 Include a description of any deception to be used in the study.*

N/A

*8.6 If the study involves long-term follow-up (once all research related procedures are complete), describe what data will be collected during the follow up period and when it will occur.*

N/A

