## 16.0 Withdrawal of Subjects

16.1 *Describe circumstances under which you anticipate subjects could be withdrawn from the research without their consent.*

- The research is canceled by the FDA or the sponsor
- Patient is unable to keep scheduled appointments
- A patient has a side effect that requires stopping the research

*16.2 If applicable, describe any procedures for orderly termination (e.g., discontinuation of a study drug or debriefing after a behavioral intervention).*

N/A

*16.3 Describe procedures that you will follow when subjects withdraw from the research, including partial withdrawal from procedures with continued data collection (e.g., participant declines to continue with regular blood draws, but continues with periodic behavioral questionnaires).*

If the patient withdraws consent to study before the time of surgery, the patient will not receive either the experimental or control treatments, and will receive standard surgical treatment. The patient's data will not be extracted from the EMR for study purposes, and the patient will not be given any of the survey materials. If a patient withdraws consent after the surgery, the patient's data will not be extracted from the EMR for analysis and the patient will be given no further survey materials. Existing survey materials will be destroyed. If patient partially withdraws from procedures after surgery, the data may be used except for that which is not completed.

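### Section 16.3 discards data already collected when a patient fully withdraws consent after surgery, so a known day-1 pain score or IOP result can leave the analysis

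*Combined protocol and SAP*

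**What the plan says.** Section 16.3 sets two rules for patients who withdraw after surgery.

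- **Full withdrawal of consent:** "If a patient withdraws consent after the surgery, the patient's data will not be extracted from the EMR for analysis", no more forms are given, and "Existing survey materials will be destroyed".
- **Partial withdrawal:** "If patient partially withdraws from procedures after surgery, the data may be used except for that which is not completed".

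Other sections determine which data the first rule reaches.

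- **Primary outcome.** Under 8.1, on post-operative day 1, "primary outcome data will be obtained by a blinded examiner" on a paper form.
- **IOP.** Under 8.3, IOP reaches the analysis by extraction from the EMR. Under 4.2, IOP at 1-2 weeks is the primary safety endpoint.
- **Paper forms.** Under 8.3, results are matched to the study ID, after which "Physical survey forms will then be confidentially discarded". No timing is given for that transcription.
- **Who knows the score.** The surgeon sees the patient on day 1 and "will examine pain and nausea scores to ensure both are well controlled". Section 8.1 also states that "The surgeon cannot be masked".
- **Duration.** Section 11.1 gives 6 months per patient. The Study Summary gives 2 weeks.

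Section 5.2 names the tests but no analysis population and no rule for missing data. Section 14.3, which asks how many patients must complete the procedures, is answered as not applicable.

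**The concern.** The treatment is given once, in theatre, and the primary outcome is complete a day later. Nearly all of the time in which a patient can withdraw falls after the primary result exists. Under the full-withdrawal rule, a decision taken in that period can remove the result from the analysis. By then the patient knows the score, and so does an unmasked surgeon.

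Randomisation does not protect against exclusions that depend on the outcome. They could act in either direction: loss of high-pain controls would shrink the estimated benefit, and loss of high-pain triamcinolone patients would enlarge it.

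The safety comparison is exposed in the same way. A patient who withdraws after an IOP rise, an infection or a hypersensitivity reaction would drop out of the between-arm comparison. That applies to the final analysis and to the review after every tenth completed patient in 21.1.

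**Working it through.** **1. What the rule reaches**

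| Data item | Where it is held | Effect of full withdrawal (16.3) |
|---|---|---|
| Day-1 pain, nausea and vomiting scores | Paper form, then study dataset (8.1, 8.3) | Form destroyed; a score already transcribed is not mentioned |
| Pill counts | Paper form, then study dataset (8.1, 8.3) | Same |
| IOP, surgical details | EMR (8.3) | Not extracted for analysis; stays in the clinical record (9.1) |

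The 1-2 week IOP endpoint is lost after it is known only if withdrawal follows that visit. Patients withdrawn without their consent under 16.1, for example for a side effect, are not covered by either rule in 16.3.

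**2. The plan's own sample size**

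Inputs from 14.1: control 3 (SD 2.5), experimental 1 (SD 1), alpha 0.01, power 0.80. The alternative hypothesis is two-sided.

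- Pooled SD = √((1² + 2.5²)/2) = 1.904, so d = 2/1.904 = 1.05, as stated.
- A two-sided t-test needs 22.9 per arm, or 46 in total. Dividing by the Mann-Whitney efficiency of 0.955 gives 22.9/0.955 = 23.98, so 24 per arm and 48 in total. The stated 48 is reproduced.
- With all 48 scores, t-test power is 0.824. With equal losses from the two arms it is 0.802 at 46, 0.779 at 44, 0.753 at 42 and 0.725 at 40. Four lost scores take it below 0.80 even without selection.

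**3. Selective loss under the planned effect**

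Assumptions: 24 per arm (the coin flip in 8.1 does not guarantee this), normal scores with the planned means and SDs, and a two-sided pooled t-test at 0.01. The k highest control scores are deleted. The figures come from simulation, with 200,000 replicates for the shifts and 100,000 for power.

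| k | Shift in control mean | Effect = 2 − shift | Power | Power, same number lost at random |
|---|---|---|---|---|
| 0 | 0 | 2.00 | 0.822 | – |
| 1 | 0.212 | 1.79 | 0.760 | 0.815 |
| 2 | 0.392 | 1.61 | 0.687 | 0.808 |
| 3 | 0.558 | 1.44 | 0.610 | 0.801 |

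Random loss costs little, so the damage comes from selection. Deleting the 1, 2 or 3 highest triamcinolone scores instead enlarges the effect by 0.08, 0.16 or 0.22 points. With scores rounded and limited to 0-10, the shifts are 0.20, 0.38 and 0.54 (control) and 0.08, 0.15 and 0.21 (triamcinolone).

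**4. Selective loss with no true effect**

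Both arms are set to mean 3, SD 2.5, and the k highest triamcinolone scores are deleted. The chance of a significant result favouring triamcinolone goes from 0.005 (k = 0) to 0.012, 0.025 and 0.043 for k = 1, 2 and 3.

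**5. Loss that ignores arm**

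If instead the k highest scores among all 48 are deleted, whatever the arm, the false-positive rate favouring triamcinolone stays at about 0.005. Power under the planned effect falls to the same 0.76, 0.69 and 0.61, because the highest scores are almost always in the control arm.

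**The case against.** The strongest reply is that the rule will rarely apply.

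- **Reach.** A patient who only stops completing forms or declines the 6-month call can be treated as a partial withdrawal, and the completed data are kept. Treatment is over, no extra visits are needed (23.1), and the $20 is paid only after the 6-month call (15.4). There is little reason to withdraw consent outright. This stands, and no withdrawal rate is documented to set against it.
- **Transcribed scores.** Read literally, 16.3 destroys forms and stops extraction but does not order deletion from the dataset. If transcription is prompt, the primary score may survive. This also stands. It means that retention would depend on when someone entered the form, which is no better as a rule.
- **The surgeon.** The rule is triggered by the patient, who is masked. The surgeon's knowledge matters only if it influences the patient's decision, and nothing in the documents suggests that it would.
- **False positives.** Inflation requires withdrawal to differ by arm. Pain-driven withdrawal that ignores arm costs power but does not favour triamcinolone, as step 5 shows. The 0.043 is an arm-dependent extreme.
- **Safety oversight.** Adverse events that may be related to the intervention still go to the IRB (21.1) and IOP stays in the clinical record (9.1). Only the between-arm comparison loses the patient.
- **Privacy.** Destroying data on full withdrawal may be a deliberate choice. Honouring express requests respects it, but does leave some outcome-dependent removal possible.

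These points limit the likely size of the problem. They do not remove the rule, and nothing in the analysis section compensates for it.

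**Conclusion.** The concern holds for full withdrawal of consent after surgery. Section 16.3 actively removes collected data, and its terms reach both the form that carries the primary score and the EMR source of the primary safety endpoint. Whether a score already transcribed would also be removed is not stated.

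The size is unknown because the number of withdrawals is unknown. At 24 per arm, one to three selective losses from the control arm would cost 0.21 to 0.56 points of a 2-point effect and 6 to 21 percentage points of power. False-positive inflation, to at most 0.043 in the cases examined, needs losses confined to the triamcinolone arm. These are worst-case illustrations under normal scores and the plan's own means and SDs. The change is worth making because it is cheap and the trial is small, not because bias has been shown.

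**What to change.** Amend 16.3 as follows.

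- Withdrawal after surgery stops further data collection only. Data collected up to that point (day-1 form, pill counts, IOP, adverse events) are kept and analysed in the randomised arm. This extends the protocol's existing partial-withdrawal rule to full withdrawal.
- The same holds for patients withdrawn under 16.1.
- State what happens to scores already transcribed to the study ID.
- Honour an express request for deletion, and report the number and timing of such requests by arm.

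The cost is one paragraph of protocol wording and possibly a consent amendment. The consent form is not in the reviewed copy, so whether it promises destruction must be checked. The downside is that patients must be told that data collected before withdrawal are kept. No visits or patients are added.

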## 17.0 Risks to Subjects

*17.1 List the reasonably foreseeable risks, discomforts, hazards, or inconveniences to the subjects related to the subjects' participation in the research.*

Adverse event data was collected by the FDA from 300 published articles containing data from controlled and uncontrolled clinical trials which evaluated over 14,000 eyes treated with different concentrations of triamcinolone acetonide. The most common dose administered within these trials was triamcinolone acetonide 40 mg administered as primary or adjunctive therapy primarily as a single injection. The most common reported adverse events following administration of triamcinolone acetonide were elevated intraocular pressure and cataract progression. These events have been reported to occur in 20-60% of patients. Less common reactions occurring in up to 2% include endophthalmitis (infectious and non-infectious), hypopyon, injection site reactions (described as blurring and transient discomfort), glaucoma, vitreous floaters, and detachment of retinal pigment epithelium, optic disc vascular disorder, eye inflammation, conjunctival hemorrhage and visual acuity reduced. Cases of exophthalmos have also been reported.

**Risk of infection:** Corticosteroids may mask some signs of infection, and new infections may appear during their use. There may be decreased resistance and inability to localize infection when corticosteroids are

## Using Triamcinolone Acetonide to Reduce Pain after Scleral Buckle Surgery

used. Corticosteroids may enhance the establishment of secondary ocular infections due to fungi or viruses. If an infection occurs during corticosteroid therapy, it will be promptly controlled by suitable antimicrobial therapy.

**Elevated Intraocular Pressure:** Increases in intraocular pressure associated with triamcinolone acetonide injection have been observed in 20-60% of patients. This may lead to glaucoma with possible damage to the optic nerve. Effects on intraocular pressure may last up to 6 months following injection and are usually managed by topical glaucoma therapy. A small percentage of patients may require aggressive non-topical treatment. Intraocular pressure as well as perfusion of the optic nerve head will be monitored and managed appropriately. As our study will be irrigating the peribulbar space rather than injecting into the posterior capsule of the eye, we expect our rate of elevated IOP to be much lower than that determined by the FDA.

**Endophthalmitis:** The rate of infectious culture positive endophthalmitis is 0.5%. Proper aseptic techniques will always be used when administering triamcinolone acetonide. In addition, patients will be monitored following the injection to permit early treatment should an infection occur.

**Cataracts:** Use of corticosteroids may produce cataracts, particularly posterior subcapsular cataracts. As our study will be irrigating the subtenon's space rather than injecting into the posterior capsule of the eye, we expect our rate of cataracts to be much lower than that determined by the FDA.

**Patients with Ocular Herpes Simplex:** Corticosteroids should be used cautiously in patients with ocular herpes simplex because of possible corneal perforation. Corticosteroids should not be used in active ocular herpes simplex. We will be excluding all patients with ocular herpes simplex.

Systemic reactions are exceedingly rare in ophthalmic administration of corticosteroids but are included below for completeness:

**Cardiovascular:** Bradycardia, cardiac arrest, cardiac arrhythmias, cardiac enlargement, circulatory collapse, congestive heart failure, fat embolism, hypertrophic cardiomyopathy in premature infants, myocardial rupture following recent myocardial infarction, pulmonary edema, syncope, tachycardia, thromboembolism, thrombophlebitis, vasculitis

**Dermatologic:** Acne, allergic dermatitis, cutaneous and subcutaneous atrophy, dry scalp, edema, facial erythema, hyper or hypo-pigmentation, impaired wound healing, increased sweating, petechiae and ecchymoses, rash, sterile abscess, striae, suppressed reactions to skin tests, thin fragile skin, thinning scalp hair, urticaria

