### 4.2 *Describe any primary or secondary safety endpoints. These should be included for all studies that are greater than minimal risk.*

- Primary: No significant difference in ocular hypertension 1-2 weeks post-operatively, defined as IOP of >5mmHg above baseline
- Secondary:
  - No significant difference in infections following surgery
  - No significant difference in hypersensitivity following surgery

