## Using Triamcinolone Acetonide to Reduce Pain after Scleral Buckle Surgery

		be applied during surgery.					
What Patient will do	Review and sign the consent document	Receive pill count form	Keep track of pain medication s taken on pill-count form	Fill out pain and nausea form. Turn in pill-count and receive second pill-count	Keep track of pain medication s taken on pill-count form	Fill out pain and nausea form. Turn in pill-count	Report pain level from 0-10

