### 8.2 *Describe:*

- *Procedures or safeguards intended to reduce the probability and magnitude of risks.*

Patients will be screened twice for IOP (measured by tonometer) post-surgically to check for ocular hypertension. Patients eyes will also be examined at both visits by the primary surgeon via slit-lamp to determine any adverse events as a result of surgery or the intervention. The surgeon is responsible for the medical safety of all patients and may prescribe any medications deemed necessary for control of side effects of surgery or intervention, including nausea and vomiting.

- *Be sure to describe all drugs and devices used in the research, when they will be administered or used, and their purpose.*  
See 7.1

*Methods used to collect data about subjects. Please upload all data collection forms to Protocol Management*

- Pain and Nausea Survey
- Pill-Count
- IOP (tonometry)

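### Study IOP data end at 1-2 weeks although section 17.1 allows for steroid pressure effects of up to 6 months, so later IOP rises will not be recorded by arm; the optic nerve head monitoring promised there is named in no procedure.

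*Combined protocol and SAP*

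**What the plan says.** On the risk, section 17.1 (Elevated Intraocular Pressure) states: "Effects on intraocular pressure may last up to 6 months following injection and are usually managed by topical glaucoma therapy". It goes on: "Intraocular pressure as well as perfusion of the optic nerve head will be monitored and managed appropriately". It gives no method, schedule or duration for that monitoring. It expects a much lower rate of raised IOP with irrigation than with injection, but says nothing about how long a rise would last after irrigation.

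On measurement:

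- The primary safety endpoint in 4.2 is "No significant difference in ocular hypertension 1-2 weeks post-operatively, defined as IOP of >5mmHg above baseline".
- The last planned reading is in 8.1: "At second post-operative visit (1-2 weeks), patients' IOP will be measured again for safety endpoint". Section 21.1 gives the same schedule: baseline, 24 hours and 2 weeks.
- Section 8.3 says: "During the study, IOP will be collected at two time-points via tonometer". It continues: "This data will be extracted from the electronic medical record for analysis".
- The examination is described in 8.2: "Patients eyes will also be examined at both visits by the primary surgeon via slit-lamp to determine any adverse events".
- At 6 months the contact is by phone. The visit table in 8.1 lists one task for the patient: "Report pain level from 0-10". Section 8.6, on long-term follow-up data, is answered N/A.

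**The concern.** Raised IOP is one of the two most common adverse events named in 17.1, and it is the primary safety endpoint. Section 3.1 says that triamcinolone acts for several months. The planned IOP data stop within two weeks, although the study already contacts each patient at 6 months.

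A rise present at 1-2 weeks would be counted. What the plan does not collect by arm is whether that rise lasted, whether a new one appeared, and whether pressure treatment was started later. Section 3.3 hopes that a positive result will help to set standard practice for pain and swelling. A finding of no difference at 1-2 weeks could then be taken as wider reassurance about pressure than the data can give.

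The second gap is one of wording. A risk section should not promise monitoring of optic nerve head perfusion if no procedure provides for it.

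**Working it through.** **Schedule against stated risk window**

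| Item | Where | Timing |
|---|---|---|
| Stated duration of IOP effect (injection) | 17.1 | up to 6 months |
| Drug's duration of action | 3.1 | several months |
| IOP readings | 8.1, 8.2, 21.1 | before surgery, day 1, 1-2 weeks |
| IOP safety endpoint | 4.2 | 1-2 weeks |
| 6-month call | 8.1 table | pain score only |
| Optic nerve head assessment | 17.1 only | none named in 8.1, 8.2, 8.3 or 21.1 |

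Taking 6 months as 182.5 days, the last reading falls at 7/182.5 = 3.8% to 14/182.5 = 7.7% of the window. About 168 days (182.5 - 14), or 5.5 months, have no planned IOP data. This is a share of time, not a share of missed events; the documents give no onset pattern from which to work out the latter.

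**Arm size**

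The plan's figure of 48 reproduces as a total. The pooled SD is √((1² + 2.5²)/2) = 1.904, so d = 2/1.904 = 1.05. With two-sided alpha 0.01 and power 0.80, the t-test needs 22.90, so 23 per arm and 46 in all. Dividing by the Mann-Whitney relative efficiency, 22.90/0.955 = 23.98, so 24 per arm and 48 in all. Section 26.1 agrees: 4 surgeries a month × 50% × 24 months = 48. That is about 24 per arm. Allocation is by coin flip, so sizes will vary; 17 to 31 in an arm covers 97% of outcomes under Binomial(48, 0.5).

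**What added data could show**

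Suppose that every patient has later data and an arm has no later rise or treatment. The exact two-sided 95% upper limit is 1 - 0.025^(1/n):

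- n = 24: 14.2%
- n = 17: 19.5%
- n = 31: 11.2%

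For 0/24 against 0/24, the Wilson upper limit in each arm is 1.96²/(24 + 1.96²) = 3.84/27.84 = 13.8%. The Newcombe 95% interval for the difference is therefore -13.8 to +13.8 percentage points. These figures measure what the fix can deliver, not the harm done by the gap.

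**The case against.** The strongest reply is that 17.1 lists foreseeable risks and is not a schedule. A reader might infer that it promises 6 months of IOP measurement and so contradicts the visit plan. It does not: the monitoring sentence has no duration, and the 6 months is stated for injection. The surgeon is responsible for patients' medical safety and may prescribe as needed (8.2), possibly related adverse events go to the IRB with no stated end date (21.1), and patients with a history of steroid-responsive IOP elevation are excluded (12.2). The documents do not support a claim that patients are left unprotected. That part of the reply stands.

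Three other strong readings also fail:

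- That the trial learns nothing about persistence. A day-1 rise is measured again at 1-2 weeks.
- That 8.3 forbids later extraction. It is not an exhaustive list: it gives two time points for pain although the plan has three, and leaves out the baseline IOP.
- That 4.2 claims general IOP safety. It already names 1-2 weeks, and 3.3 speaks of pain and swelling.

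What the reply does not remove is narrower. Clinical care may deal with a late rise, but no planned data item tabulates it by arm, and the documents offer no shorter duration for irrigation. It is also fair to say that 48 patients cannot settle late safety. That argues for descriptive reporting and a time-limited conclusion, rather than for collecting nothing.

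**Conclusion.** The point holds as a cheap improvement. It does not touch the sample size, alpha or the primary pain analysis. As planned, the trial will have no systematic by-arm record of IOP rises that persist, appear or need treatment after week 2, in a period of about 5.5 months that the protocol's own injection figure leaves open. Separately, one phrase in 17.1, on optic nerve head perfusion, has no matching procedure.

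This rests on two assumptions: that the injection duration is relevant to irrigation, which the documents neither confirm nor rule out, and that later readings and treatments are at least partly present in the EMR. No rate of late events is claimed. I have not seen section 6.0 (Setting) and infer nothing from it.

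**What to change.** 1. In 8.3, add extraction from the EMR, in both arms and up to 6 months, of all IOP values and any IOP-lowering treatment. Record timing as days since surgery, because the box for elements of dates in 9.5 is unticked. Leave out patients who withdrew consent, as 16.3 requires.
2. Add one question to the existing 6-month call, worded identically in both arms: has any eye-pressure treatment been started since surgery?
3. Report descriptively by arm, with counts, 95% intervals and the number of patients with any reading after week 2. This supplements the 1-2 week endpoint and does not replace it.
4. In the study report, limit the IOP safety conclusion from the 4.2 endpoint to 1-2 weeks.
5. Keep the commitment in 17.1 to monitor and manage. Cutting it to match the data schedule would remove a patient safeguard. Either state that the optic nerve head is assessed at the existing surgeon examinations, or drop only the word perfusion.

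The cost is a longer run of an extraction already planned, using the re-identification code that the principal investigator holds until publication (9.4), plus one question; the consent text may need a line. There is no extra visit or procedure, so 23.1 remains true. The downside is that routine readings will be uneven and sometimes missing, and the surgeon who takes them and decides on treatment is unmasked (8.1), so arm differences may partly reflect who was checked.

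The mismatch between 2 weeks of enrolment in 1.0 and 6 months in 11.1 is a separate wording correction.

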## 12.0 Inclusion and Exclusion Criteria

### 12.1 Describe how you will screen individuals for eligibility. When will screening occur and what procedures will you use? Upload any screening scripts or surveys to Protocol Management.

Individuals will be screened at time of diagnosis. All patients who are determined to need scleral buckle surgery for rhegmatogenous retinal detachment will be screened for eligibility. Screening for the trial will be done by the surgeon, who will be reviewing the medical history at time of visit via EMR. If patient does not fail the exclusion criteria, the patient will be consented for enrollment in the trial. There are no screening scripts or surveys that will be used.

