### 12.2 Describe the eligibility criteria that define who will be included and who will be excluded from enrollment for each procedure of your study.

Inclusion Criteria: Patient must have rhegmatogenous retinal detachment and be scheduled to undergo scleral buckle surgery for correction.

Exclusion Criteria:

- Patient under 18 years old
- Advanced Glaucoma
- History of corticosteroid responsive elevation in IOP
- Allergy to Triamcinolone Acetonide or other corticosteroids
- Pre-existing chronic pain disorders
- Herpes zoster
- Prior corneal allograft
- Allergy to local anesthetic or penicillin

- Patients unable to consent on own behalf
- Patients unable to communicate pain and nausea levels
- Pregnancy
- Incarceration

*12.3 Indicate specifically whether you will include or exclude each of the following special populations: (You may not include members of these populations as subjects in your research unless you indicate them in the description of your subject population.)*

All of the following populations will be excluded from our study.

- *Minors, as defined by state law where the study is performed (infants, children, teenagers)*
- *Pregnant women*
- *Prisoners (including all incarcerated individuals)*
- *Adults not capable to consent on their own behalf*

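### Section 17.1 promises to exclude ocular herpes simplex, but the section 12.2 exclusion list names only herpes zoster

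*Combined protocol and SAP*

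**What the plan says.** Section 17.1 has a separate paragraph on ocular herpes simplex. It advises caution because the cornea may perforate, adds that "Corticosteroids should not be used in active ocular herpes simplex", and ends with the commitment "We will be excluding all patients with ocular herpes simplex".

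Section 12.2 sets out the eligibility criteria. Its only herpes entry is "Herpes zoster". Herpes simplex appears neither there nor among the special populations in 12.3.

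Section 12.1 describes how the criteria are used. The surgeon reviews the history in the electronic record, and "If patient does not fail the exclusion criteria, the patient will be consented for enrollment in the trial". It adds that "There are no screening scripts or surveys that will be used".

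Under section 8.1, enrolled patients are "randomized (by coin-flip) into one of two arms, the control or the experimental". The experimental arm receives 1 ml of triamcinolone at 40 mg/mL under the tenon layer.

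**The concern.** An exclusion works only if it is applied at screening, and in this protocol screening runs on the exclusion criteria in 12.2. The other steroid-related exclusions (advanced glaucoma, previous steroid-induced pressure rise, corticosteroid allergy) are all there. The herpes simplex exclusion is not, and herpes zoster does not stand in for it.

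Two things are at stake. The first is patient safety: the list does not screen for a contraindication that the protocol itself states. The second is the accuracy of what an ethics board reads. From 17.1 it would conclude that a protection exists which the screening procedure does not implement. Enrolling such a patient would comply with 12.2 and breach 17.1.

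**Working it through.** This is mainly a comparison of text, with one short calculation.

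**1. Could another criterion catch the patient?**

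| Provision | Catches ocular herpes simplex? |
|---|---|
| 12.2 inclusion (rhegmatogenous detachment, buckle scheduled) | No |
| 12.2 "Herpes zoster" | No, a different disease |
| 12.2 "Prior corneal allograft" | Only a patient who already has a graft |
| 12.3 special populations | No |
| 12.1 record review | Only if the surgeon looks for something the list does not name |

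**2. Could a later safeguard catch the patient?** Section 8.2 relies on pressure checks after surgery and on slit-lamp examination: "Patients eyes will also be examined at both visits by the primary surgeon via slit-lamp to determine any adverse events". Both visits come after the steroid has been given. Section 3.1 puts triamcinolone's duration of action at several months, and 17.1 notes that corticosteroids can mask signs of infection. The last scheduled eye examination is at 1-2 weeks. The 6-month contact is a telephone call for a pain score (8.1).

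**3. Do the two sections contradict each other?** No. Both exclusions can apply together, so this is an omission from the list. The list reads as complete in the text available, so a redaction or extraction gap does not explain it.

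**4. Probability of exposure.** Input: a coin flip between two arms (8.1), so P(triamcinolone) = 0.5 for each enrolled patient. If k patients with ocular herpes simplex are enrolled,

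P(at least one receives triamcinolone) = 1 − 0.5^k

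- k = 1: 1 − 0.5 = 0.50
- k = 2: 1 − 0.25 = 0.75
- k = 3: 1 − 0.125 = 0.875

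The documents do not give k, so these figures are conditional on enrolment. They do not estimate the risk in this trial.

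**5. Sample size.** The plan gives no figure on this point. Its N of 48 (14.1) was checked only to confirm that it stands apart from the issue.

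- Pooled SD = √((1² + 2.5²)/2) = 1.904, so d = 2/1.904 = 1.05.
- A two-sided t-test at alpha 0.01 and power 0.80 needs 22.9, rounded up to 23 per arm, or 46 in total.
- Dividing 22.9 by the Mann-Whitney relative efficiency 3/π = 0.955 gives 24 per arm, or 48.

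No eligibility criterion enters this calculation.

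**The case against.** The strongest reply is that the protocol does exclude these patients. Section 17.1 says so flatly, and enrolling one requires a surgeon to apply one section and ignore another. Screening is done by a surgeon, not a clerk. Section 15.1 describes the recruiters as knowing the patients' histories and possible drug complications. Section 26.1 says the two surgeons already understand the drugs and risks and plans a meeting before the study starts. Section 8.2 makes the surgeon responsible for patients' medical safety. This lowers the risk, but none of it names herpes simplex. Section 26.1 also counts four operating surgeons and describes only two as already informed.

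Three further points deserve weight.

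- **Unseen scripts.** A recruitment script (15.1) and a consent script (24.1) exist and were not available. They might mention herpes simplex, but neither is described as an eligibility check, and 12.1 rules out screening scripts.
- **No excess exposure shown.** Section 3.3 says multiple surgeons already give triamcinolone at every scleral buckle operation. No excess over usual practice is claimed here, and the documents do not say how herpes simplex patients are treated outside the trial.
- **Reach of the fix.** Section 17.1 does not mention past disease, and it reserves its outright prohibition for active disease. However, it distinguishes ocular herpes simplex in general from the active form and then excludes everyone with the condition. Covering any history is therefore a fair reading, but the sponsor should confirm it.

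**Conclusion.** The concern holds and should be corrected. Followed literally, the enrolment gate in 12.1 and 12.2 admits a patient whom 17.1 says will be excluded, and that patient has a 50% chance of receiving the study steroid. The textual mismatch is certain. The number of patients affected is unknown and likely small with 48 planned.

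The conclusion rests on two assumptions: that the coin is fair, and that a surgeon may apply the 12.2 list as it stands without bringing in the sentence from 17.1. The priority comes from the severity of the harm that the protocol names and from how little the correction costs, not from an estimated event rate.

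**What to change.** - Add a separate line to 12.2: ocular herpes simplex, active or any history. The sponsor should confirm that past disease is meant to be covered.
- Apply it at the record review in 12.1, before consent.
- State whether the zoster entry is a criterion in its own right or a slip for simplex.
- Keep the commitment in 17.1. Deleting it would make the sections agree but leave a stated contraindication unscreened.
- Make the change before screening starts or, if it has started, before the next patient is screened.

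The cost is one line and one clarifying phrase. Sample size and analysis are unaffected. The effect on recruitment is likely negligible: section 26.1 gives 4 operations a month, so 4 × 24 = 96 over two years, of which 48 (50%) are needed. For an affected patient, the chance of receiving study triamcinolone falls from 0.5 to 0 once the criterion is applied.
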